8.3 Safety Data Handling

Definition of derived variables for extent of exposure

The derivation rule will be presented in the [section 5.6.1](#).

Treatment-emergent adverse event

A treatment-emergent adverse event (TEAE) is defined as an AE that emerges during time from the first dose of study drug to the last visit or 28 days after the subject's last dose, whichever comes later, having been absent at pretreatment (Baseline) or

- Reemerges during treatment, having been present at pretreatment (Baseline) but stopped before treatment, or
- Worsens in severity during treatment relative to the pretreatment state, when the AE is continuous.

TEMAV (Treatment-Emergent Markedly Abnormal Value)

A TEMAV is defined as follows:

- For a phosphate, if the post baseline grade increases from baseline and the post baseline grade is greater than or equal to 3 then a value will be determined to be a TEMAV.
- For all other parameters presented in the [section 13.1](#), if the post baseline grade increases from baseline and the post baseline grade is greater than or equal to 2 then a value will be determined to be a TEMAV.

If the grade of baseline value is missing, then, if the grade of post-baseline value is Grade 2 or higher, the laboratory values will be classified into treatment emergent markedly abnormal.

Laboratory values, Vital signs, ECGs

For the end of treatment, the closest value measured on or post to the last disposition date in the Treatment Phase and the entire study period will be imputed using Last Observation Carried Forward (LOCF) method. If there is no adequate data, the closest value observed prior to the disposition date is selected.

Handling of below lower quantification values in laboratory results

In the cases where laboratory result contains below lower quantification (BLQ) value, it will be replaced to the lower limit value of quantification (LLOQ) for summary tables.

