#### 9.7.1.8.3 LABORATORY VALUES

Laboratory results will be summarized using Système International (SI) units, as appropriate. For all quantitative parameters, the actual value and the change from baseline to each postbaseline visit will be summarized by visit using descriptive statistics. Qualitative parameters will be summarized using frequencies (number and percentage of subjects), and changes from baseline to each postbaseline visit will be reported using shift tables. Percentages will be based on the number of subjects with both nonmissing baseline and relevant postbaseline results.

Laboratory test results will be assigned a low/normal/high (LNH) classification according to whether the value was below (L), within (N), or above (H) the laboratory parameter's reference range. Within-treatment comparisons for each laboratory parameter will be based on shift tables that compare the baseline LNH classification to the LNH classification at each postbaseline visit.

Appendix 1 (Sponsor's Grading for Laboratory Values) presents the criteria that will be used to identify subjects with treatment-emergent markedly abnormal laboratory values (TEMAVs). Except for phosphate, a TEMAV is defined as a postbaseline value with an increase from baseline to a grade of 2 or higher. For phosphate, a TEMAV was defined as a postbaseline value with an increase from baseline to a grade of 3 or higher. The definition of TEMAV will be detailed in the SAP. When displaying the incidence of TEMAVs, each subject may be counted once in the laboratory parameter high and in the laboratory parameter low categories, as applicable.

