8.1 General Data Handling

Definition of Baseline data

Baseline is defined as the last non-missing value observed on or prior to the first study drug dispensing date.

Definition of Change from Baseline, Percent Change from Baseline

- Change from baseline = Post-baseline value - Baseline value
- % Change from baseline = (Change from baseline / Baseline value) * 100

For any baseline value of 0, the subject’s corresponding percent change from baseline will not be included in the summary statistics table.

Handling of data not within specified periods or within the follow-up period

Data obtained in the Follow-up Phase except for AE, Duration of Exposure and TEMAV will not be included in the summary tables. These data will be presented in the subject data listing.

Definition of End of Treatment

End of treatment phase during the 26-week Maintenance Period of the last evaluated dose is defined as the closest value observed on or post to the disposition date in the 26-week Maintenance Period of the last evaluated dose. If there is no adequate data, the closest value observed prior to the disposition date is selected.

End of treatment during the entire study (treatment phase or extension phase) is defined as the closest value observed on or post to the last disposition date in the entire study. If there is no data, the closest value observed prior to the last disposition date is selected.

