Phosphate, serum-low (hypophosphatemia)	<LLN – 2.5 mg/dL <LLN – 0.8 mmol/L	<2.5 – 2.0 mg/dL <0.8 – 0.6 mmol/L	<2.0 – 1.0 mg/dL <0.6 – 0.3 mmol/L	<1.0 mg/dL <0.3 mmol/L

Sponsor's Grading for Laboratory Values

	Grade 1	Grade 2	Grade 3	Grade 4
Potassium, serum-high (hyperkalemia)	>ULN – 5.5 mmol/L	>5.5 – 6.0 mmol/L	>6.0 – 7.0 mmol/L	>7.0 mmol/L
Potassium, serum-low (hypokalemia)	<LLN – 3.0 mmol/L	N/A	<3.0 – 2.5 mmol/L	<2.5 mmol/L
Sodium, serum-high (hyponatremia)	>ULN – 150 mmol/L	>150 – 155 mmol/L	>155 – 160 mmol/L	>160 mmol/L
Sodium, serum-low (hyponatremia)	<LLN – 130 mmol/L	N/A	<130 – 120 mmol/L	<120 mmol/L
Triglyceride, serum-high (hypertriglyceridemia)	150 – 300 mg/dL 1.71 – 3.42 mmol/L	>300 – 500 mg/dL >3.42 – 5.7 mmol/L	>500 – 1000 mg/dL >5.7 – 11.4 mmol/L	>1000 mg/dL >11.4 mmol/L
Uric acid, serum-high (hyperuricemia)	>ULN – 10 mg/dL ≤0.59 mmol/L	N/A	N/A	>10 mg/dL >0.59 mmol/L

ALP = alkaline phosphatase, ALT = alanine aminotransferase (serum glutamic pyruvic transaminase), AST = aspartate aminotransferase (serum glutamic oxaloacetic transaminase), GGT = γ -glutamyl transpeptidase, N/A = not applicable, LLN = lower limit of normal, ULN = upper limit of normal, WBC = white blood cell.

Based on Common Terminology Criteria for Adverse events (CTCAE) Version 4.0. Published: May 28, 2009 (v4.03: June 14, 2010).

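### The SAP's missing-baseline rule for markedly abnormal laboratory values (TEMAVs) flags phosphate at Grade 2, although the phosphate threshold is Grade 3 in both documents

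*SAP*

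**What the plan says.** SAP 8.3 defines a TEMAV by two bullets. The first is for phosphate: "For a phosphate, if the post baseline grade increases from baseline and the post baseline grade is greater than or equal to 3". The second is for every other parameter in the grading table: "if the post baseline grade increases from baseline and the post baseline grade is greater than or equal to 2". Protocol 9.7.1.8.3 sets the same higher threshold: "For phosphate, a TEMAV was defined as a postbaseline value with an increase from baseline to a grade of 3 or higher". The protocol has no rule for a missing baseline and leaves the detail of the TEMAV definition to the SAP.

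After both bullets, SAP 8.3 adds a separate paragraph: "If the grade of baseline value is missing, then, if the grade of post-baseline value is Grade 2 or higher", the result counts as markedly abnormal. It refers to laboratory values in general.

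SAP 13.1 gives phosphate Grade 2 as "<2.5 – 2.0 mg/dL <0.8 – 0.6 mmol/L". SAP 8.1 fixes the baseline: "Baseline is defined as the last non-missing value observed on or prior to the first study drug dispensing date".

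For low bicarbonate, SAP 13.1 and Protocol Appendix 1 print the same bands: Grade 1 from below the lower limit of normal (LLN) down to 16, Grade 2 from 11 to 15, Grade 3 from 8 to 10, and Grade 4 below 8 mmol/L. Neither document states the reporting precision or a rounding rule.

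**The concern.** Both documents single out phosphate for a higher threshold, so Grade 2 phosphate was evidently not meant to count. The missing-baseline paragraph lowers that threshold by one grade for subjects about whom less is known, and gives no reason. A programmer following the SAP has to choose between two sentences that disagree, and that choice decides whether such a subject appears in the TEMAV table.

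The bicarbonate question is separate and sits in the grading table, not in the TEMAV rule. Its bands are whole numbers with open space between 10 and 11 and between 15 and 16. No other row leaves a gap between adjacent grades: leukocytes, for example, share the cut-points 3.0, 2.0 and 1.0. If decimals are reported, a low result could fall outside every grade and so outside the TEMAV count.

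**Working it through.** The plan gives no figure to reproduce here, so the check is to apply the rules literally.

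**Phosphate.** Inputs are the two bullets and the missing-baseline paragraph in SAP 8.3, with the grades in SAP 13.1.

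- Baseline known: TEMAV if the post-baseline grade exceeds the baseline grade and is at least 3.
- Baseline missing, as written: TEMAV if the post-baseline grade is at least 2.
- Baseline missing, using phosphate's own threshold: TEMAV if the post-baseline grade is at least 3.

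| Post-baseline phosphate grade | Baseline Grade 0, 1 or 2 | Baseline missing, as written | Baseline missing, own threshold |
|---|---|---|---|
| 0 or 1 | No | No | No |
| 2 | No | **Yes** | No |
| 3 or 4 | Yes | Yes | Yes |

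One cell differs. To one decimal, it holds results of 2.0 to 2.4 mg/dL.

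For every other parameter the paragraph fits its bullet. With baseline Grade 0 or 1, the bullet flags any post-baseline grade of 2 or more, and the missing-baseline rule flags the same grades. The paragraph therefore acts as if a missing baseline were unremarkable. For phosphate, that logic gives Grade 3.

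**How often it can apply.** Protocol Table 3 schedules laboratory tests at Visits 1 and 2, both before treatment, and baseline is the last non-missing value. The allowance in footnote i, for local analysis at Visit 1, covers bicarbonate and magnesium but not phosphorus. Under footnote m, same-day Visits 1 and 2 need only one sample. The conflict therefore needs a treated subject with no usable phosphate from one or two planned samples, and a later Grade 2 result.

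**Bicarbonate.** The documents give no LLN, so 18, 20, 22 and 24 mmol/L were tried as assumptions. The result was the same for each:

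- Whole-number results: every value has a grade.
- Results to 0.1 mmol/L: 10.1 to 10.9 (9 values) and 15.1 to 15.9 (9 values) have none, so 9 + 9 = 18.

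The two gaps differ in consequence:

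- Between 10 and 11, the neighbouring grades are 3 and 2. Both reach the TEMAV threshold if the grade rose from baseline, so an ungraded 10.5 is missed whichever was meant. The less abnormal value of 11 is Grade 2 and can be flagged.
- Between 15 and 16, the neighbours are 2 and 1. Grade 1 is never a TEMAV, so whether anything is missed depends on the intended grade.

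With decimals, an ungraded bicarbonate at baseline could also be taken as a missing baseline grade. A later Grade 2 value would then be flagged with no rise in grade shown.

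**The case against.** The intent on phosphate is clear, since both documents state Grade 3. One could also read the missing-baseline sentence as belonging to the second bullet only. SAP 8 lets the sponsor settle data handling before database lock, and SAP 9 places derivation rules in separate specifications not available here. Clear intent shows which sentence should change, but the sentence still contradicts it. It stands as its own paragraph after both bullets and refers to laboratory values generally, so the narrow reading is not what is written.

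The strongest objection is rarity, and it stands as to size. A reader might infer that the TEMAV table will over-count phosphate. The documents do not support that: nothing indicates that any treated subject will lack a pre-dose value.

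A reader might also infer that the SAP misclassifies low bicarbonate. That goes too far. The printed bands are complete for whole-number results, and decimal reporting is not stated. Even with decimals, a missed TEMAV is clear only between 10 and 11 mmol/L. SAP 5.6.3 lists each result's low, normal or high class, so a low bicarbonate without a grade would still appear in the listings.

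It is tempting to close the gaps by following the other rows, which would make 15.5 Grade 2 and 10.5 Grade 3. Beyond that convention, the documents give no support for those grades. Both tables cite CTCAE version 4.0 as their source, and it was not available for this review.

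**Conclusion.** The phosphate contradiction is real and rests on the SAP text alone. Applied literally, a Grade 2 phosphate is a TEMAV when baseline is missing and is not one when baseline is known. The importance is minor: only descriptive safety tables are affected, efficacy analyses are untouched, and the cases should be few. The documents give no basis for estimating a number.

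The bicarbonate point is secondary. It holds only if results carry decimals, and it is best treated as a query about precision and rounding.

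**What to change.** In SAP 8.3, change the missing-baseline threshold to *Grade 2 or higher (Grade 3 or higher for phosphate)*. This is one added phrase. It brings the sentence into line with the phosphate bullet and Protocol 9.7.1.8.3, and changes no other classification.

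For bicarbonate, confirm the laboratory's reporting precision. If decimals are reported, either state a rounding rule to apply before grading, or make the bands contiguous after checking the source scale. Do not assign the gap values to a grade by assumption.

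Both edits can be made in the SAP and noted in SAP 7 before database lock. SAP 13.1 already departs from Protocol Appendix 1 in places (low potassium Grade 2 and uric acid Grade 3 are not applicable in the SAP), so a protocol amendment need not be the route. The cost is a short text edit, one query to the laboratory, and a check that the programming specifications match.

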8.4 Pharmacokinetic Data Handling

8.4.1 Lower Limit of Quantification of Perampanel Plasma Concentration

The LLOQ of perampanel plasma concentrations is 0.250 ng/mL.

8.4.2 BLQ Handling for Calculation of PK Parameters

Not applicable

8.4.3 BLQ Handling for Developing Concentration-Time Profiles

Not applicable

8.4.4 Handling of Anomalous Concentration Values

The handling of anomalous concentration values will follow the guidance in the Eisai manual 302-104.00-MNL for non compartmental PK analysis (Version Date: 08 Jun 2016).

8.4.5 General Rules for Presentation of Drug Concentrations and PK Parameters

When presenting individual/raw (raw, hereafter) values and summary statistics, the following rule will be applied: for drug concentrations, all summary statistics (mean, median, and standard deviation [SD]) will have 3 significant digits.

Variable	Unit	N	Digit rule	Raw/ Minimum/ Maximum	Mean Median	SD	Geometric Mean	CV (%)
Perampanel concentration	ng/mL	X	Significant digits	3	3	3	-	-

9 PROGRAMMING SPECIFICATIONS

The rules for programming derivations and dataset specifications are provided in separate documents.

10 STATISTICAL SOFTWARE

All statistical analyses will be conducted by the designee, using validated standard programs or double programming. For analyses needed in data review, single programming will be used.

All statistical analyses will be performed using SAS (version 9.2 or later). As necessary, other validated statistical software will also be used.

11 MOCK TABLES, LISTINGS, AND GRAPHS

The study TLG shells will be provided in a separate document, which will show the content and format of all tables, listings, and graphs in detail.

13 APPENDICES

13.1 Sponsor's Grading for Laboratory Values

The following table of Eisai's Grading for Laboratory Values is based on the [Protocol Appendix 1](#).

Sponsor's Grading for Laboratory Values

	Grade 1	Grade 2	Grade 3	Grade 4
BLOOD/BONE MARROW				
Hemoglobin	<LLN – 10.0 g/dL <LLN – 100 g/L <LLN – 6.2 mmol/L	<10.0 – 8.0 g/dL <100 – 80 g/L <6.2 – 4.9 mmol/L	<8.0 g/dL <80 g/L <4.9 mmol/L	N/A
Leukocytes (total WBC)	<LLN – 3.0×10 ⁹ /L <LLN – 3000/mm ³	<3.0 – 2.0×10 ⁹ /L <3000 – 2000/mm ³	<2.0 – 1.0×10 ⁹ /L <2000 – 1000/mm ³	<1.0×10 ⁹ /L <1000/mm ³
Lymphocytes	<LLN – 800/mm ³ <LLN – 0.8×10 ⁹ /L	<800 – 500/mm ³ <0.8 – 0.5×10 ⁹ /L	<500 – 200/mm ³ <0.5 – 0.2×10 ⁹ /L	<200/mm ³ <0.2×10 ⁹ /L
Neutrophils	<LLN – 1.5×10 ⁹ /L <LLN – 1500/mm ³	<1.5 – 1.0×10 ⁹ /L <1500 – 1000/mm ³	<1.0 – 0.5×10 ⁹ /L <1000 – 500/mm ³	<0.5×10 ⁹ /L <500/mm ³
Platelets	<LLN – 75.0×10 ⁹ /L <LLN – 75,000/mm ³	<75.0 – 50.0×10 ⁹ /L <75,000 – 50,000/mm ³	<50.0 – 25.0×10 ⁹ /L <50,000 – 25,000/mm ³	<25.0×10 ⁹ /L <25,000/mm ³
METABOLIC/LABORATORY				
Albumin, serum- low (hypoalbuminemia)	<LLN – 3 g/dL <LLN – 30 g/L	<3 – 2 g/dL <30 – 20 g/L	<2 g/dL <20 g/L	N/A
ALP	>ULN – 3.0×ULN	>3.0 – 5.0×ULN	>5.0 – 20.0×ULN	>20.0×ULN
ALT	>ULN – 3.0×ULN	>3.0 – 5.0×ULN	>5.0 – 20.0×ULN	>20.0×ULN
AST	>ULN – 3.0×ULN	>3.0 – 5.0×ULN	>5.0 – 20.0×ULN	>20.0×ULN
Bicarbonate, serum-low	<LLN – 16 mmol/L	11 – 15 mmol/L	8 – 10 mmol/L	<8 mmol/L
Bilirubin (hyperbilirubinemia)	>ULN – 1.5×ULN	>1.5 – 3.0×ULN	>3.0 – 10.0×ULN	>10.0×ULN
Calcium, serum-low (hypocalcemia)	<LLN – 8.0 mg/dL <LLN – 2.0 mmol/L	<8.0 – 7.0 mg/dL <2.0 – 1.75 mmol/L	<7.0 – 6.0 mg/dL <1.75 – 1.5 mmol/L	<6.0 mg/dL <1.5 mmol/L
Calcium, serum-high (hypercalcemia)	>ULN – 11.5 mg/dL >ULN – 2.9 mmol/L	>11.5 – 12.5 mg/dL >2.9 – 3.1 mmol/L	>12.5 – 13.5 mg/dL >3.1 – 3.4 mmol/L	>13.5 mg/dL >3.4 mmol/L
Cholesterol, serum-high (hypercholesterolemia)	>ULN – 300 mg/dL >ULN – 7.75 mmol/L	>300 – 400 mg/dL >7.75 – 10.34 mmol/L	>400 – 500 mg/dL >10.34 – 12.92 mmol/L	>500 mg/dL >12.92 mmol/L
Creatinine	>ULN – 1.5×ULN	>1.5 – 3.0×ULN	>3.0 – 6.0×ULN	>6.0×ULN
GGT (γ-glutamyl transpeptidase)	>ULN – 3.0×ULN	>3.0 – 5.0×ULN	>5.0 – 20.0×ULN	>20.0×ULN
Glucose, serum-high (hyperglycemia)	>ULN – 160 mg/dL >ULN – 8.9 mmol/L	>160 – 250 mg/dL >8.9 – 13.9 mmol/L	>250 – 500 mg/dL; >13.9 – 27.8 mmol/L	>500 mg/dL; >27.8 mmol/L
Glucose, serum-low (hypoglycemia)	<LLN – 55 mg/dL <LLN – 3.0 mmol/L	<55 – 40 mg/dL <3.0 – 2.2 mmol/L	<40 – 30 mg/dL <2.2 – 1.7 mmol/L	<30 mg/dL <1.7 mmol/L
Phosphate, serum-low (hypophosphatemia)	<LLN – 2.5 mg/dL <LLN – 0.8 mmol/L	<2.5 – 2.0 mg/dL <0.8 – 0.6 mmol/L	<2.0 – 1.0 mg/dL <0.6 – 0.3 mmol/L	<1.0 mg/dL <0.3 mmol/L

Sponsor's Grading for Laboratory Values

	Grade 1	Grade 2	Grade 3	Grade 4
Potassium, serum-high (hyperkalemia)	>ULN – 5.5 mmol/L	>5.5 – 6.0 mmol/L	>6.0 – 7.0 mmol/L	>7.0 mmol/L
Potassium, serum-low (hypokalemia)	<LLN – 3.0 mmol/L	N/A	<3.0 – 2.5 mmol/L	<2.5 mmol/L
Sodium, serum-high (hyponatremia)	>ULN – 150 mmol/L	>150 – 155 mmol/L	>155 – 160 mmol/L	>160 mmol/L
Sodium, serum-low (hyponatremia)	<LLN – 130 mmol/L	N/A	<130 – 120 mmol/L	<120 mmol/L
Triglyceride, serum-high (hypertriglyceridemia)	150 – 300 mg/dL 1.71 – 3.42 mmol/L	>300 – 500 mg/dL >3.42 – 5.7 mmol/L	>500 – 1000 mg/dL >5.7 – 11.4 mmol/L	>1000 mg/dL >11.4 mmol/L
Uric acid, serum-high (hyperuricemia)	>ULN – 10 mg/dL ≤0.59 mmol/L	N/A	N/A	>10 mg/dL >0.59 mmol/L

ALP = alkaline phosphatase, ALT = alanine aminotransferase (serum glutamic pyruvic transaminase), AST = aspartate aminotransferase (serum glutamic oxaloacetic transaminase), GGT = γ -glutamyl transpeptidase, N/A = not applicable, LLN = lower limit of normal, ULN = upper limit of normal, WBC = white blood cell.

Based on Common Terminology Criteria for Adverse events (CTCAE) Version 4.0. Published: May 28, 2009 (v4.03: June 14, 2010).
